7.2 Dose Interruption

In Period 2, if a participant is unable to be dosed at a visit, all other assessments planned for that visit per the SoA ([Section 1.2](#)) should still be conducted as planned with the exception of PK samples which do not need to be collected. If participant is unable to come to clinic for a visit, that entire visit will be skipped.

If a TEAE caused the second dose to be skipped for a participant in Period 2, it should have resolved or returned to baseline before the participant is restarted on study treatment after consultation with the Sponsor's Medical Monitor.

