^g Predose plasma PK at every dosing visit. Specific time points for PK and select laboratory Weeks 0 and 4 provided in [Table 6](#). Participants should stay in the clinic for 48 hours after the first and last doses to complete assessments.

- ^h Full physical examination includes (at a minimum): alertness and orientation, general appearance, skin, head, eyes, ears, nose, throat, lungs, cardiovascular, gastrointestinal, musculoskeletal, and neurologic systems. Symptom-directed physical examinations to be performed as necessary.
- ⁱ Height at Screening will be used for BMI calculations at all visits.
- ^j Vital signs will be taken with the participant in the supine position after ≥ 5 minutes of rest. Temperature, respiratory rate, and SpO₂ are measured once per time point. Blood pressure (systolic and diastolic) and pulse: measured ≤ 30 minutes pre-dose and 1 hr (± 10 min), 2 hr (± 10 min), 4 hr (± 20 min), 12 hr (± 1 hr) post dose on Day 1 and once at all other noted visits. Should additional post dose vital signs be collected per Site SOP, these should be captured in eCRF.
- ^k Continuous digital ECG monitoring for at least 48 hours from Day -1 through Day 2 and at least 24 hours through first day of last dose (Day 29); leads may be disconnected for ~ 20 minutes following 24 hours after the first dose to allow for participant cleansing. Additional triplicate 12-lead ECGs are specified in [Table 7](#). Note: only predose triplicate ECGs are required at Day 15. Participant must rest quietly for ≥ 5 minutes prior to triplicate ECGs.
- ^l For drug screen panel, see [Table 11](#) other screening tests.
- ^m Following the second dose (Week 2) all participants will be observed for safety evaluation in the clinic for at least 4 hours post study drug administration or per local SOP (whichever is longer).

Table 6 Plasma PK and Selected Laboratory Time Points (Period 2)

Study Day/Specific Time	Days 1, 15, 29	Days 1 and 29							Days 2 and 30		Days 3 and 31	Weeks 1 through 16
	Pre-dose	Post dose										
	≤ 30 min prior to dose ^b	30 min (± 5 min)	1 hr (± 5 min)	2 hr (± 5 min)	4 hr (± 10 min)	6 hr (± 10 min)	8 hr (± 10 min)	12 hr (± 10 min)	24 hr (± 30 min)	36 hr (± 4 hr)	48 hr (± 4 hr)	Visits 3 through 15
Plasma PK ^a	X	X	X	X	X	X	X	X	X	X	X	Every visit
CBC, CRP, fibrinogen, coagulation, albumin	X					X			X Day 2 only		X Day 3 only	Every visit
Complement	X			X	X	X			X Day 2 only		X Day 3 only	Weeks 1, 5, 6, and 8 only

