3 OBJECTIVES, ENDPOINTS, AND ESTIMANDS

Table 8 Study Objectives and Endpoints for WVE-006-001

Primary Objective:	Primary Endpoint:

 To evaluate the safety and tolerability of WVE-006 	
 Incidence of treatment emergent adverse events (TEAEs), related TEAE, severe TEAE, serious TEAE Changes in safety assessment parameters (i.e., physical exam, vital signs, clinical laboratory results, ECGs (including any changes to QTcF)) Tolerability based on incidence of discontinuation due to TEAEs
Secondary Objective:	Secondary Endpoints:

 To evaluate the PK of WVE-006 after a single dose in healthy participants To evaluate the PK of WVE-006 after multiple doses in healthy participants 	
 PK parameters of WVE-006 in plasma, including AUC_{inf}, AUC_{0-24h}, AUC_{0-48h}, AUC_{last}, C_{max}, t_{max} PK parameters of WVE-006 in plasma following the first and last doses, including AUC_{tau}, AUC_{0-24h}, AUC_{0-48h}, AUC_{last}, C_{max}, t_{max}
Exploratory Objectives:	Exploratory Endpoints:

 To evaluate urine excretion of WVE-006 	
 Ae, Ae%, and cumulative Ae% (cum Ae%) for parent drug, as well as potential metabolites in urine

Abbreviations: Ae=amount excreted; AUC=area under the curve; C=concentration; ECG=electrocardiogram; PK=pharmacokinetic; t=time; TEAE=treatment-emergent adverse event

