In Period 2, a single cohort of up to 8 healthy participants, including up to 6 WVE-006 and up to 2 placebo treated participants (3:1 active:placebo), will participate in a multidose assessment of WVE-006. A sentinel strategy will be employed for the first 2 participants (1 active:1 placebo), with a 48-hour observation period to assess for acute safety events. The DEC and DMC will review available safety and PK data from Period 1 to select the MTD with an acceptable PK profile. The MTD is defined as the dose below a dose level where any of the dose escalation stopping rules were met. If MTD is not achieved in Period 1 (i.e., no dose escalation stopping rules were met and all doses were well tolerated), then the highest dose reached in Period 1 will likely be selected for Period 2, though the DEC and DMC may select a lower dose based on all available information. At least 4 weeks of safety data for the proposed dose and all available data from the study must be available from Period 1 in order to inform the DEC and DMC Period 2 dose selection. WVE-006 or placebo will be administered every other week (Q2W) over 4 weeks (total of 3 doses; Weeks 0, 2, and 4). Following the first dose (Week 0) and last dose (Week 4), participants will stay in the clinic for at least two nights for PK assessments. Following the second dose (Week 2) all participants will be observed for safety evaluation in the clinic for at least 4 hours post-study drug administration or per local SOP (whichever is longer).

In Period 2, dosing will be paused or discontinued (per Investigator judgment) for an individual participant; see [Section 7.1.1](#) for additional details.

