8.5 Pharmacokinetic Assessments

- Blood samples will be collected for measurement of plasma concentrations of WVE-006 and for potential analysis of metabolites as specified in the SoA ([Table 2](#) and [Table 6](#)). The actual date and time (24-hour clock time) of each sample will be recorded. Instructions for the collection and handling of biological samples will be provided by the Sponsor in a Laboratory Manual.
 - Plasma and urine samples for analysis of exposure to WVE-006 will be collected at the time points specified in [Table 2](#), [Table 3](#), and [Table 6](#). Samples will be collected at the following time points:
 - Period 1 Plasma PK: Samples will be collected predose within 30 min prior to dose, and postdose at 30 min (± 5 min), 1 hr (± 5 min), 2 hr (± 5 min), 4 hr (± 10 min), 6 hr (± 10 min), 8 hr (± 10 min), 12 hr (± 10 min), 24 hr (± 30 min), 36 hr (± 4 hr), and 48 hr (± 4 hr). A sample will be collected at each of the following visits: Days 8, 15, 22, 29, 36, 43, 50, 57, 64, 71, 78 (± 3 days), and Day 85 (± 5 days)/ET.
 - Period 1 Urine PK: Samples will be collected over 0-4 hr, 4-8 hr, 8-12 hr, 12-18 hr, 18-24 hr, 24-36 hr, and 36-48 hr.
 - Period 2 Plasma PK: Day 1 and Day 29 samples will be collected predose within 30 min prior to dose, and postdose at 30 min (± 5 min), 1 hr (± 5 min), 2 hr
-

(± 5 min), 4 hr (± 10 min), 6 hr (± 10 min), 8 hr (± 10 min), 12 hr (± 10 min), 24 hr (± 30 min), 36 hr (± 4 hr), and 48 hr (± 4 hr). A Day 15 predose sample will be collected at 30 min prior to dose. A sample will be collected at each of the following visits: Days 8, 21, 36, 43, 50, 57, 64, 71, 78, 85 (± 3 days) and Day 113 (± 5 days) / ET.

- Urine samples will be collected for measurement of concentration of WVE-006 and potential metabolites as specified in the SoA (Table 3). The following parameters will be estimated for the parent drug:
 - Ae: amount excreted in urine
 - Ae%: the percentage of the administered dose that is excreted in urine
 - Cum Ae%: cumulative Ae%
- The timing of sampling may be altered, and PK samples may be obtained at additional time points during the course of the study based on newly available data (e.g., to obtain data nearer the time of peak plasma concentration) to ensure appropriate monitoring of the PK profile.
- Blood samples will be used to evaluate the PK profile of WVE-006 assessed by the following PK parameters, if applicable:
 - AUC_{inf}: area under the curve from time 0 to infinity

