 - AUC_{0-24h}: area under the curve from time 0 to 24 hours
 - AUC_{0-48h}: area under the curve from time 0 to 48 hours
 - AUC_{last}: area under the curve from time 0 to the last measurable concentration
 - AUC_{ext}: area under the curve extrapolated to infinity
 - AUC_{tau}: area under the curve over a dosing interval
 - C_{max}: maximum observed concentration
 - t_{max}: time to occurrence of C_{max}
 - t_{1/2}: terminal half-life
 - V_d: volume of distribution
 - CL: clearance
- Samples collected for analyses of WVE-006 plasma concentration may also be used to evaluate safety aspects arising during or after the study.
- PK information that would unblind the study will not be reported to investigative sites or blinded personnel until the study has been unblinded.

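### Section 7.2 makes the pre-dose PK sample optional when a Period 2 dose is withheld, so first-dose AUCtau may lack an observed value at the end of its interval

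*Combined protocol and SAP*

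**What the plan says.** Section 7.2 (Dose Interruption) deals with a Period 2 participant who attends a visit but cannot be dosed. Everything else planned for the visit goes ahead, "with the exception of PK samples which do not need to be collected". No distinction is made between pre-dose and post-dose samples. The same section foresees one cause: "If a TEAE caused the second dose to be skipped for a participant in Period 2".

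The sampling and endpoint provisions that this touches are:

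- Section 4.1.2: dosing is every other week, "total of 3 doses; Weeks 0, 2, and 4".
- Section 3, Table 8: the multiple-dose secondary endpoint is "PK parameters of WVE-006 in plasma following the first and last doses, including" AUCtau. Section 8.5 defines AUCtau as "area under the curve over a dosing interval".
- Section 8.5, Period 2 plasma PK: serial samples to 48 h after the Day 1 and Day 29 doses; "A Day 15 predose sample will be collected at 30 min prior to dose"; and "A sample will be collected at each of the following visits: Days 8, 21, 36, 43, 50, 57, 64, 71, 78, 85", then Day 113. Day 15 is not in that list of visits.
- Section 1.3, Table 5 footnote g: "Predose plasma PK at every dosing visit".
- Section 1.3, Table 6: plasma PK at each of Visits 3 through 15, a range that includes Visit 4 (Day 15) and Visit 6 (Day 29).
- Section 8.5 also says that plasma PK samples may serve to evaluate safety aspects.

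**The concern.** Waiving the serial samples is sensible when no dose is given. The pre-dose sample is different: at Day 15 it is the 336 h concentration after the first dose, and it is the only sample scheduled at the end of the first dosing interval. Its value does not depend on whether dose 2 follows. Section 7.2 nevertheless makes it optional at a visit where other blood is still drawn.

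Three things are at stake. First-dose AUCtau loses its observed closing value in a group of at most 6 active participants. The loss can depend on safety, because a TEAE is one reason for withholding the dose. And a concentration becomes optional in a participant with such an event, although Section 8.5 allows samples to be used for safety evaluation.

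The instructions also pull in different directions. Table 6 asks for PK at every one of Visits 3 through 15, footnote g ties the pre-dose sample to a dosing visit, and Section 7.2 waives it. Two sites could act differently and both be following the protocol.

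**Working it through.** There is no stated figure to reproduce: the sample size is not based on a hypothesis test, and no rule is given for AUCtau when the end-of-interval sample is absent.

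**Sampling times after the first dose** (hours = (Day − 1) × 24):

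- End of interval: tau = 14 × 24 = 336 h, which is Day 15
- Day 8: 7 × 24 = 168 h
- Day 21: 20 × 24 = 480 h

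| | Last point before 336 h | Next point | Gap |
|---|---|---|---|
| Day 15 sample taken | 168 h | 336 h | 168 h |
| Day 15 sample waived | 168 h | 480 h | 480 − 168 = 312 h |

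The part of tau after the last required point is 336 − 168 = 168 h, or 168/336 = 50% of the interval.

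**How much AUC lies in that half.** The documents do not give the terminal half-life, so this is a range under assumptions. Assumed curve: C(t) = (1 − f)·g(k_fast) + f·g(k_slow), with g(k) = ka/(ka − k)·(e^(−kt) − e^(−ka·t)), ka = 0.5/h, fast half-life 4 h, slow half-life 24 to 672 h, and slow fraction f from 0.1% to 10%. Share of AUC(0–336 h) falling in 168–336 h:

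| Slow half-life | f = 0.1% | f = 1% | f = 10% |
|---|---|---|---|
| 24 h | 0.005% | 0.05% | 0.3% |
| 72 h | 0.3% | 2.5% | 11.1% |
| 168 h | 1.0% | 8.1% | 26.2% |
| 336 h | 1.7% | 12.4% | 34.4% |
| 672 h | 2.1% | 15.2% | 38.9% |

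**What can be recovered if dose 2 is skipped.** Day 21 then still reflects dose 1 alone and brackets 336 h. Over the same grid, compared with having the Day 15 sample:

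- log-linear interpolation between Day 8 and Day 21: error 0.00%
- linear interpolation: overstatement of 0.01% to 3.0%
- curve cut at Day 8: loss of up to 38.7%

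The log-linear result is almost exact partly because the assumed tail is log-linear. It also needs both concentrations to be quantifiable. If dose 2 is instead given before Day 21, Day 21 no longer reflects dose 1 alone, but footnote g calls for a pre-dose sample at the visit where dosing takes place.

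**How often.** The documents give no rate of missed doses. For an assumed chance p that an active participant misses dose 2, the chance of at least one case among 6 is 1 − (1 − p)^6: 27% for p = 5%, 47% for p = 10%, 74% for p = 20%.

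**Day 29 withheld.** The first interval is unaffected. The Day 15 dose becomes the last dose, and the waived sample is the one 14 × 24 = 336 h after it. Its neighbours are Day 21 (6 × 24 = 144 h after that dose) and Day 36 (21 × 24 = 504 h). No serial samples follow the Day 15 dose in any case, so what is lost here is mainly a trough concentration.

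**The case against.** The strongest reply is that nothing essential is lost. The waiver is permissive and a site may still draw the tube. Day 21 brackets the end of the interval when dose 2 is skipped, and a late dose brings its own pre-dose sample. Cmax, tmax, AUC0-24h and AUC0-48h after the first dose are untouched. Period 1 also supplies single-dose concentrations through Day 15 at the dose level carried forward. PK is summarised descriptively, and a more detailed SAP is due before database lock. Most of this stands, and it limits the consequence.

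A reader might infer that first-dose AUCtau becomes missing and that the active group falls from 6 to 5. The documents do not support that, because the Day 21 sample is scheduled and may allow an estimate. A reader might also infer that the affected participants are often adverse-event cases, or that their concentration data are discarded. Section 7.2 contains one conditional sentence about a TEAE and no frequency, and the waiver covers only the visit without a dose; sampling resumes at the following visits.

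The reply does not remove the point itself. Section 7.2 is an explicit rule, so the required sampling leaves the interval open. The freedom in Section 8.5 to re-time or add samples is optional and not linked to missed doses. A later SAP can set an interpolation rule but cannot recover a sample that was never drawn. Period 1 data come from other participants, while Table 8 places this endpoint in the multiple-dose cohort.

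**Conclusion.** The point holds in limited form. When the Week 2 dose is withheld at an attended visit, the plan does not require the only sample scheduled at 336 h. The sampling gap across the end of the interval widens from 168 h to 312 h, and first-dose AUCtau rests on interpolation or extrapolation that is not prespecified. It is less well observed, not necessarily missing.

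The size cannot be fixed from the documents. It is negligible if plasma concentrations are already very low by Day 8, or if Day 8 and Day 21 are both quantifiable and the decline between them is log-linear. It is material if a slow phase persists and the curve has to be cut at Day 8. The 0.005% to 39% range rests wholly on the assumed curves. Dependence of the missing value on safety is possible but not demonstrated. This is a cheap improvement to a stated rule and does not threaten the trial's conclusions.

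**What to change.** Amend Section 7.2 so that, at any attended Period 2 visit where the dose is withheld, the scheduled pre-dose PK sample is still collected with its actual date and time, and only the serial post-dose samples are omitted. Align Table 6 and Table 5 footnote g with that wording, so that it is clear the sample is due whether or not the dose is given. The same sentence covers both Day 15 and Day 29.

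The cost is one extra plasma tube per affected visit. Table 6 already schedules pre-dose blood on those days for blood count, CRP, coagulation, complement and cytokines, and Section 7.2 keeps those draws. The change concerns data collection only and alters no dosing or restart rule.

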7.3 Lost to Follow-up

Participants who fail to return for assessments will be contacted by the site in an attempt to have them comply with the protocol. A minimum of 3 documented contact efforts should be made on different days over the course of 2 weeks. If site requirements to consider a participant lost to follow-up are more stringent, the site requirements must be fulfilled. Contact efforts can include phone call, text message, email, or contacting the participant's partner (if applicable). If the participant is unreachable, a registered letter will be sent to the participant requesting him or her to contact the study center. If contact with the participant is not established after all above attempts, this participant will be considered as lost to follow-up.

7.4 Replacements

In Period 1 or 2, additional participants may be enrolled as replacements for discontinued or withdrawn participants (refer to [Section 7](#)) in consultation with the Sponsor.

Any participants enrolled but withdrawn prior to the first dose will be replaced. Any participants withdrawn or discontinued after receiving at least one dose may be replaced at the discretion of the Sponsor.

Enrollment/randomization numbers will not be reused. A new, unique enrollment/randomization number will be given to the new participant.

8 STUDY ASSESSMENTS AND PROCEDURES

Study procedures and their timing are summarized in [Section 1.2](#). Additional details of each assessment are given below. Screening assessments must meet eligibility criteria as listed in [Section 5](#). Deviations from protocol procedures are not allowed unless required to protect the immediate safety of the participant. In such instances, the Investigator should make every attempt to discuss the need with the Sponsor's Medical Monitor in advance, but no later than within 24 hours after the deviation was implemented. The safety reason(s) for the deviation should be documented.

Results of assessments will be recorded in the eCRF and source documents. In general, any assessment or result the Investigator considers clinically significant should be recorded as an AE.

8.1 General Baseline and Administrative Assessments

8.1.1 Medical History and Demographics

A general medical history will be obtained at the Screening Visit. Investigator assessment of past medical history at Screening will include information regarding any significant medical, surgical, and psychiatric conditions and treatments.

Demographic data will be collected.

8.1.2 Height and Weight

The participant's height and weight will be measured at the time points described in the SoA. To the extent possible, the same scale should be used through the study. BMI will be automatically calculated based on the entered height and weight and will not need to be manually entered.

8.1.3 Eligibility Criteria Review

The Investigator will review the participant's social history, Screening laboratory, and other assessments to confirm that the participant meets all eligibility criteria.

8.1.4 Drug, Alcohol, and Cotinine Screening

A commercially available urine drug screen, alcohol breath or urine test, and cotinine screen will be conducted at the time points described in the SoA. Screening results must meet eligibility criteria. Positive results while the participant is on study must be recorded in the participant's medical record and discussed with the Medical Monitor.

Participants will be instructed to not eat food containing poppy and/or sesame seeds for 3 days before each visit to the Clinical Unit, as consumption of poppy and/or sesame seeds can lead to a positive opiate result in the drugs of abuse test.

8.1.5 Follicle Stimulating Hormone

FSH testing will be done at Screening only as needed to confirm a female participant is not of child-bearing potential.

8.1.6 Viral Serology

Viral serology for hepatitis B, hepatitis C and HIV 1/2 (where testing for HIV is permitted per local regulations) will be conducted at Screening to confirm the participant meets eligibility criteria.

8.1.7 COVID-19 Testing

If applicable, COVID-19 testing will be performed per site SOP at Screening and/or on Day -1 to ensure the participant meets eligibility criteria. Additional COVID-19 testing may be performed if required during the conduct of the study, per site SOPs, at other visits.

8.2 Efficacy Assessments

There are no efficacy assessments as this HV study is focused on safety and PK.

8.3 Safety Assessments

The safety assessments will include the following:

- AEs
- Concomitant medications
- Full and symptom-directed physical examinations
- Vital signs
- Weight / BMI
- Digital continuous and triplicate 12-lead ECGs
- Clinical laboratory evaluations (as per [Table 11](#))
- Pregnancy testing (if applicable)

Strenuous exercise must be completely avoided from 3 days before the first dose of study drug until the final study visit.

See [Section 10.3](#) to determine if abnormal laboratory test results or other safety assessments qualify as AEs.

8.3.1 Prior and Concomitant Medications

It is the responsibility of the Investigator to ensure that details regarding the medication(s) are recorded in full in the eCRF. Refer to [Section 6.10](#) for more details regarding prior and concomitant medications.

8.3.2 Physical Examination

At Screening, a full physical examination will include (but is not limited to) an examination of skin, head, eyes, ears, nose, throat, respiratory, cardiovascular, gastrointestinal, endocrine, metabolic, blood, lymphatic, musculoskeletal, psychiatric, and neurologic (including mental status, cranial nerves, motor system, reflexes, coordination and gait, and sensory system) systems. A full physical examination is required at other visits, as noted in the SoA.

At some time points, a symptom-directed physical examination will include systems to be evaluated as appropriate for the participant's condition and symptoms.

8.3.3 Vital Signs

Vital sign measurements will be taken with the participant in a supine position after the participant has been resting quietly for a period of at least 5 minutes. Blood pressure (systolic and diastolic), temperature, pulse, respiratory rate, and SpO₂ will be measured by qualified personnel at the time points described in the SoA. If the initial reading is high, the measurements will be repeated once to confirm the results.

